9.10 Early phase safety monitoring

The Investigator will monitor adverse events in an ongoing manner and inform the Sponsor of any clinically relevant observations. Any required safety reviews will be made jointly between medically qualified personnel representing the Sponsor and Investigator. Such evaluations may occur verbally, but the outcome and key discussion points will be summarized in writing (e-mail) and made available to both Sponsor and all Investigator(s). Criteria pertaining to stopping the study/treatment or adapting the study design are presented above.

When two or more clinical site(s) are participating in the clinical study, the Sponsor will advise the Investigator(s) at all sites in writing (e-mail) (and by telephone if possible) of any new, clinically relevant safety information reported from another site during the conduct of the study in a timely manner.

10 Data review and database management

10.1 Site monitoring

Before study initiation, at a site initiation visit or at an investigator's meeting, a Novartis representative will review the protocol and CRFs with the investigators and their staff. During the study, Novartis employs several methods of ensuring protocol and GCP compliance and the quality/integrity of the sites' data. The monitor will visit the site to check the completeness of subject records, the accuracy of entries on the CRFs, the adherence to the protocol and to Good Clinical Practice, the progress of enrollment, and ensure that study drug is being stored, dispensed, and accounted for according to specifications. Key study personnel must be available to assist the monitor during these visits.

The investigator must maintain source documents for each subject in the study, consisting of case and visit notes (hospital or clinic medical records) containing demographic and medical information, laboratory data, electrocardiograms, and the results of any other tests or assessments. All information on CRFs must be traceable to these source documents in the subject's file. The investigator must also keep the original informed consent form signed by the subject (a signed copy is given to the subject).

[figure not shown]
The investigator must give the monitor access to all relevant source documents to confirm their consistency with the CRF entries. Novartis monitoring standards require full verification for the presence of informed consent, adherence to the eligibility criteria, documentation of SAEs, and the recording of data that will be used for all primary and safety variables. Additional checks of the consistency of the source data with the CRFs are performed according to the study-specific monitoring plan. No information in source documents about the identity of the subjects will be disclosed.

10.2 Data collection

Designated investigator staff will enter the data required by the protocol into the Electronic Case Report Forms using fully validated software that conforms to 21 CFR Part 11 requirements. Designated investigator site staff will not be given access to the EDC system until they have been trained. Validation checks for data discrepancies and, by generating appropriate error messages, allow the data to be confirmed or corrected before transfer of the data to Novartis or the CRO working on behalf of Novartis. The Investigator must certify that the data entered into the Electronic Case Report Forms are complete and accurate. After database lock, the investigator will receive copies of the subject data for archiving at the investigational site.

Data not requiring a separate written record will be defined in the SOM and [Assessment schedule](#) and can be recorded directly on the CRFs. All other data captured for this study will have an external originating source (either written or electronic) with the CRF not being considered as source.

All data should be recorded, handled and stored in a way that allows its accurate reporting, interpretation and verification.

10.3 Database management and quality control

Novartis staff review the data entered into the CRFs by investigational staff for completeness and accuracy and instruct the site personnel to make any required corrections or additions. Queries are sent to the investigational site via the EDC system. Designated investigator site staff is required to respond to the query and confirm or correct the data. If the electronic query system is not used, a paper Data Query Form will be faxed to the site. Site personnel will complete and sign the faxed copy and fax it back to Novartis staff who will make the correction to the database. The signed copy of the Data Query Form is kept at the investigator site.

Concomitant medications entered into the database will be coded using the WHO Drug Reference List, which employs the Anatomical Therapeutic Chemical classification system. Medical history/current medical conditions and adverse events will be coded using the Medical dictionary for regulatory activities (MedDRA) terminology.

Laboratory results will be sent electronically to Novartis (or a designated CRO).

The occurrence of any protocol deviations will be determined. After these actions have been completed and the database has been declared to be complete and accurate, it will be locked and made available for data analysis. Any changes to the database after that time can only be made by joint written agreement between the COAR Analytics NIBR Franchise Head and the relevant NIBR TA Head.

[figure not shown]

10.4 Data Monitoring Committee

Not applicable.

10.5 Adjudication Committee

An Adjudication Committee will be established to assess suspected cases of ketoacidosis as described in the SOM.

11 Data analysis

11.1 Analysis sets

For all analysis sets, subjects will be analyzed according to the study treatment(s) received.

The safety analysis set will include all subjects that received any study drug.

The PK analysis set will include all subjects with at least one available valid (i.e. not flagged for exclusion) PK concentration measurement, who received any study drug and with no protocol deviations that impact on PK data.

The PD analysis set will include all subjects with available PD data and no protocol deviations with relevant impact on PD data.

11.2 Subject demographics and other baseline characteristics

All data for background and demographic variables will be listed by renal function (mild impairment, Grade A moderate impairment, Grade B moderate impairment, severe impairment, or normal) and subject. Summary statistics will be provided by renal function.

Relevant medical history, current medical conditions, results of laboratory screens, drug tests and any other relevant information will be listed by renal function and subject.

11.3 Treatments

Data for study drug administration (rescue medication) and concomitant therapies will be listed renal function and subject.

[figure not shown]
11.4 Analysis of the primary variable(s)

11.4.1 Variable(s)

The primary PD endpoint will be UGE24.

The primary PK endpoints will be the C_{max}, T_{max}, AUC_{tau}, AUC_{last}, AUC_{inf}, T_{1/2}, CL/F of LIK066.

The secondary PK endpoints will be V_z/F and CL_r of LIK066.

11.4.2 Statistical model, hypothesis, and method of analysis

The primary analyses will assess the effect of reduced renal function on UGE24 and on the PK of LIK066.

UGE24

The change from baseline in UGE24 will be analyzed using an analysis of covariance (ANCOVA) model with diabetic status, renal impaired group, day, and all associated interactions (where possible) as fixed factors and age, baseline body weight, and baseline fasting plasma glucose as covariates. Baseline fasting plasma glucose and baseline body weight will be the measurements on Day 1 0-hour. An unstructured covariance matrix will be used.

The least-square mean change from baseline will be estimated for each diabetic status by renal function by day combination. In addition, the mean difference between each renal impaired group and the group with normal renal function and the corresponding two-sided 90% confidence interval and p-value for the difference will be extracted for each diabetic status by day combination.

UGE24 will be summarized by diabetic status, renal function, and day. The change from baseline and % change from baseline will also be summarized.

The relationship between eGFR and UGE24 will be assessed graphically, separately by day.

PK

Each of the log-transformed PK parameters (C_{max} , AUC_{tau} , AUC_{last} , AUC_{inf} as applicable) will be analyzed using the same model described above for UGE24 but without the baseline covariates. For each parameter, the least-square geometric mean will be estimated for each diabetic status by renal function by day combination. In addition, the geometric mean ratio of each renal impaired group to the group with normal renal function (expressed as a percent relative difference) and the corresponding two-sided 90% confidence interval and p-value for the ratio will be extracted for each diabetic status by day combination.

Statistical analysis may be performed to compare the free fraction (f_u) across the treatment groups. If statistically significant difference exists in f_u across treatment groups, the same analysis (as planned for total parameters) will also be performed to compare the AUC_{u} and $C_{max,u}$ between treatment groups.

The summary of PK parameters is described below in [Section 11.4.4](#).

11.4.3 Handling of missing values/censoring/discontinuations

All drug concentrations below the lower limit of quantification (LLOQ) will be reported as “zero” and will be treated as zero for calculation of PK parameters. No other imputation of missing values will be performed.

11.4.4 Summary statistics of pharmacokinetics

LIK066 plasma concentration data will be listed by renal function, subject, and visit/sampling time point. Descriptive statistics will be provided by renal function and visit/sampling time point, including the frequency (n, %) of concentrations below the LLOQ and reported as zero. Summary statistics will include mean (arithmetic and geometric), SD, CV (arithmetic and geometric), median, minimum, and maximum. Concentrations below LLOQ will be treated as zero in the summary statistics. A geometric mean will not be reported if the dataset includes zero values.

Each of the PK parameters will be listed by renal function, subject, and day and summarized by renal function and day. Descriptive statistics will include mean (arithmetic and geometric), SD, CV (arithmetic and geometric), median, minimum, and maximum. An exception to this is T_{max} where median, minimum, and maximum will be presented.

11.4.5 Sensitivity analyses

Two sensitivity analyses of UGE24 may be performed:

(1) a similar analysis as the primary UGE analysis, except that natural logarithm of the ratio to baseline in UGE24 will be modeled instead of the change from baseline. For this analysis, the least-square geometric mean will be estimated for each diabetic status by renal function by day combination, in addition to the geometric mean ratio of each renal impaired group to the group with normal renal function (expressed as a percent relative difference) and the corresponding two-sided 90% confidence interval and p-value, separately for each diabetic status by day combination.

(2) the same analysis described for the primary UGE analysis, except that baseline UGE24 will be used as a covariate in place of baseline fasting plasma glucose. Baseline UGE24 will be the collection taking place on Day -1. The same model-based quantities described for the primary analysis will be extracted.

11.5 Analysis of secondary variable(s)

11.5.1 Efficacy / Pharmacodynamics

See [Section 11.4.2](#).

[figure not shown]
11.5.2 Safety

Vital signs

All vital signs data will be listed by renal function, subject, and visit/time and if ranges are available abnormalities (and relevant orthostatic changes) will be flagged. Summary statistics will be provided by renal function and visit/time.

ECG evaluations

All ECG data will be listed by renal function, subject and visit/time, abnormalities will be flagged. Summary statistics will be provided by renal function and visit/time.

Clinical laboratory evaluations

All laboratory data will be listed by renal function, subject, and visit/time and if normal ranges are available abnormalities will be flagged. Summary statistics will be provided by renal function and visit/time.

Adverse events

[figure not shown]
All information obtained on adverse events will be displayed by renal function and subject.

The number and percentage of subjects with adverse events will be tabulated by body system and preferred term with a breakdown by renal function. A subject with multiple adverse events within a body system is only counted once towards the total of this body system.

Anion gap

[figure not shown]
From measurements of sodium, chloride, and bicarbonate in serum, the anion gap will be derived as sodium – (chloride + bicarbonate) and will be an additional safety variable. The anion gap and change from baseline in anion gap will be summarized by diabetic status, renal function, and day.

[figure not shown]
[figure not shown]
For each subject, the maximum post-baseline value and the maximum change from baseline will be extracted and will be summarized by diabetic status and renal function.

11.5.3 Pharmacokinetic / pharmacodynamic interactions

The relationship between UGE24 [REDACTED] and each of the primary PK parameters may be assessed graphically, in addition to the relationship between eGFR and each of the primary PK parameters.

11.7 Sample size calculation

The sample size was chosen to provide adequate precision around the estimated mean difference in change from baseline UGE24 between a renal impaired group and the group of normal controls.

After 7 days of treatment of LIK066 15 mg once daily in patients with type-2 diabetes in the first-in-human study LIK066X2101, the mean and standard deviation of the change from baseline in UGE24 was approximately 98 g and 24 g respectively. If we observe similar variability in this study, with 10 enrolled subjects in the mild and moderate renal impaired groups and in the group of normal controls and at least 8 completers in each of these groups, a two-sided 90% CI for the difference of means will extend no more than 22.7 g from the observed difference. As an example, in the renal impairment study for the SGLT2 inhibitor empagliflozin (Macha et al 2014), the observed difference between the moderate impaired group and the normal controls was 42 g, representing a 43% decrease in UGE24. If we see a similar reduction in our study, the CI for the difference would extend to no more than 19.3 g to 64.7 g. We consider this as adequate precision for the estimation of the difference in change from baseline UGE24 between the groups.

[figure not shown]
The sample size also provides adequate precision for a comparison of the primary PK variables between groups. After a single dose of LIK066 50 mg in healthy volunteers in LIK066X2101, the coefficient of variation of the C_{max} of LIK066 was approximately 22%. Assuming similar variability in this study, with at least 8 completers in each group, a two-sided 90% CI for the ratio of means will have a lower bound that extends to no less than 0.81 times the observed ratio and an upper bound to no more than 1.23 times the observed ratio. We consider this as adequate precision for the estimation of the ratio of C_{max} between the groups.

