The template shows the analysis / results to be presented in the FIR. Study outputs required to be created at the time of the FIR will be highlighted in TFL shells document and marked as “Key” in the Programming Deliverables Tracker (PDT) output list.

FIR will focus on the following analyses:

- Analysis of populations (if needed)
- Subject disposition
- Demographics and baseline characteristics. Baseline characteristics include, but not limited to:
 - Age, Weight/Height/BMI, Diabetes status, UGE24
- Safety results include, but are not limited to:
 - Number and percentage of subjects with adverse events by body system and preferred term with a breakdown by renal function
- Pharmacokinetic (PK) results for plasma:
 - Arithmetic mean (SD) plasma PK concentration-time plot per renal function (overlying).
 - Summary statistics for PK parameters.
- Pharmacodynamic (PD) analyses include, but are not limited to:

- Model estimated renal function comparison in UGE24, change from baseline and % change from baseline in UGE24.
- Arithmetic mean (SD) UGE24 plot per renal function (overlying) over time

3 Interim analyses

An interim analysis may be initiated once approximately half of the enrolled subjects have completed the study. The purpose of the analysis will be to assess the impact of reduced renal function on UGE24 in order to inform development decisions for LIK066. Actions such as early termination of the study should objectives be met, adjustments to the sample size, and/or revisions of the dose may be made.

Additional interim analyses may be conducted to support decision making concerning the current clinical study, the sponsor’s clinical development projects in general or in case of any safety concerns. The clinical team may communicate interim results to relevant Novartis teams for information, consulting and/or decision purposes.

4 Statistical methods: Analysis sets

For all analysis sets, subjects will be analyzed according to the study treatment(s) received.

The safety analysis set will include all subjects that received any study drug.

The PK analysis set will include all subjects with at least one available valid (i.e. not flagged for exclusion) PK concentration measurement, who received any study drug and experienced no protocol deviations that impact on PK data.

The PD analysis set will include all subjects with available PD data, who received any study drug and experienced no protocol deviations with relevant impact on PD data.

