5.2 Descriptive analyses

LIK066 plasma concentration data will be listed by renal function, diabetic status, subject, and visit/sampling time point. Descriptive statistics will be provided by renal function and visit/sampling time point, including the frequency (n, %) of concentrations below the LLOQ and reported as zero.

Summary statistics will include mean (arithmetic and geometric), SD, CV (arithmetic and geometric), median, minimum, and maximum. Concentrations below LLOQ will be treated as zero in the summary statistics. A geometric mean will not be reported if the dataset includes zero values.

Each of the PK parameters will be listed by renal function, subject, and day and summarized by renal function and day. Descriptive statistics will include mean (arithmetic and geometric), SD, CV (arithmetic and geometric), median, minimum, and maximum. An exception to this is T_{max} where median, minimum, and maximum will be presented.

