5.3 Statistical model, assumptions and hypotheses

The natural logarithm of each PK parameter will be analyzed using a MMRM model with diabetic status, renal function group, day, and all associated interactions (where possible) as fixed factors and age as covariate. An unstructured covariance matrix will be used.

For each parameter, the least-square geometric mean will be estimated for each diabetic status by renal function by day combination. In addition, the geometric mean ratio of each renal impaired group to the group with normal renal function and the corresponding two-sided 90%

confidence interval and p-value for the ratio will be extracted for each diabetic status by day combination.

Statistical analysis may be performed to compare the free fraction (f_u) across the renal function groups. If statistically significant difference exists in f_u across renal function groups, the same analysis (as planned for total parameters) will also be performed to compare the $AUC_{0-\infty,u}$ and $C_{max,u}$ between renal function groups. [REDACTED]

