6.1.3 Statistical model, assumptions and hypotheses

The primary PD analysis will assess the effect of reduced renal function on UGE24.

The change from baseline in UGE24 will be analyzed using a MMRM with diabetic status, renal function group, day, and all associated interactions (where possible) as fixed factors and age, baseline body weight, and baseline fasting plasma glucose as covariates. Baseline fasting plasma glucose and baseline body weight will be the measurements on Day 1 0-hour. An unstructured covariance matrix will be used.

The least-square mean change from baseline will be estimated for each diabetic status by renal function by day combination. In addition, the mean difference between each renal impaired group and the group with normal renal function (or other least severe group with data) and the corresponding two-sided 90% confidence interval and p-value for the difference will be extracted for each diabetic status by day combination.

Additionally, the change from baseline in UGE24 will be analyzed for the overall group, using a MMRM with diabetic status, renal function group, day, and interaction terms of renal function*day and diabetic*day as fixed factors and age, baseline body weight and baseline fasting plasma glucose as covariates. An unstructured covariate matrix will be used.

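### The precision in protocol 11.7 describes whole renal groups, but the visible plan gives the PK ratios to normal only within each diabetic status, where intervals are wider

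*Protocol*

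**What the plan says.** **Sample size.** Protocol 11.7 compares a renal impaired group with the normal controls. It takes an SD of 24 g for change from baseline in UGE24, 10 enrolled and at least 8 completers in the mild, moderate and normal groups, and concludes that "a two-sided 90% CI for the difference of means will extend no more than 22.7 g from the observed difference". For Cmax it takes a CV of 22% and at least 8 completers per group, and states that "a two-sided 90% CI for the ratio of means will have a lower bound that extends to no less than 0.81 times" the observed ratio, with an upper bound of at most 1.23 times. The severe group is up to 10 patients, with no minimum stated.

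**PK analysis.** Protocol 11.4.2 fits diabetic status, renal group, day and their interactions where possible. For the ratio of each impaired group to normal, the 90% CI and "p-value for the ratio will be extracted for each diabetic status by day combination". SAP 5.3 has the same: "confidence interval and p-value for the ratio will be extracted for each diabetic status by day combination". Its visible text ends in a redaction just after the free-fraction comparison. The PK parameter output pooled over diabetic status is descriptive: "Each of the PK parameters will be listed by renal function, subject, and day and summarized by renal function and day" (SAP 5.2).

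**UGE24 analysis.** Protocol 11.4.2 and SAP 6.1.3 also extract the difference from normal within each diabetic status by day. SAP 6.1.3 then goes further: "Additionally, the change from baseline in UGE24 will be analyzed for the overall group", with a model that has no renal function by diabetic status interaction. It lists no estimate or interval from that model. SAP 6.1.3.1 repeats both supportive UGE24 analyses for overall diabetic status.

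**Diabetic mix.** Protocol 3.1 expects about half of each impaired group to have T2DM. Normal subjects are matched on diabetic status only where possible.

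**The concern.** The only stated justification for the sample size is the width of a confidence interval for whole groups. The intervals that the plan lists for comparison with normal come from diabetic subsets of those groups. PK is one of the two primary objectives. A reader of 11.7 may attach 0.81–1.23 to the PK ratios that will be reported, yet no visible PK contrast has that precision in both diabetic statuses. UGE24 has a planned model that can meet its limit, but the text does not say that the limit belongs to that model.

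**Working it through.** **Inputs.** SD 24 g, from T2DM patients at 15 mg, and Cmax CV 22%, from healthy volunteers (both protocol 11.7). 8 completers or 10 enrolled per group. Assumption: both values hold in each diabetic status. The documents give no SD for subjects without diabetes.

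**Formulas.** UGE24 half-width = t(0.95, df) × SD × √(1/n1 + 1/n2). For Cmax, σ(log) = √ln(1 + 0.22²) = 0.2174, and the multipliers are exp(∓ t × σ × √(1/n1 + 1/n2)).

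**1. The plan's own figures.** For 8 vs 8, √(1/8 + 1/8) = 0.5. With 7 df, t = 1.895:
- UGE24: 1.895 × 24 × 0.5 = 22.73 g.
- Cmax: exp(∓ 1.895 × 0.2174 × 0.5) = 0.814 to 1.229.

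Both match 11.7.

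**2. The by-status contrasts.** I used the variance pooled over the whole model, which favours the plan. The df are subjects minus 10 cells minus covariates (3 for UGE24, 1 for PK in the SAP), with all five groups at the stated size.

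| Impaired vs normal, one diabetic status | df (UGE24 / Cmax) | UGE24 | Cmax |
|---|---|---|---|
| 4 vs 4 (half of 8) | 27 / 29 | ±28.9 g | 0.77–1.30 |
| 5 vs 5 (half of 10, no dropout) | 37 / 39 | ±25.6 g | 0.79–1.26 |
| 4 vs 2 | 27 / 29 | ±35.4 g | 0.73–1.38 |

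If only the two cells being compared supply the variance (df 6 at 4 vs 4), the result is ±33.0 g and 0.74–1.35. With no normal subjects in a status, the contrast with normal cannot be estimated.

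**3. Does another split help?** For group size N, 1/n + 1/(N−n) ≥ 4/N. The two statuses' values of (1/n1 + 1/n2) therefore sum to at least 8/N, and the larger is at least 4/N: 0.50 at N = 8 and 0.40 at N = 10. Even with z = 1.645, the limits need at most (22.7/(1.645 × 24))² = 0.331 for UGE24 and (ln 1.23/(1.645 × 0.2174))² = 0.335 for Cmax. So none of the 81 splits of 8 vs 8 or the 121 splits of 10 vs 10 meets either limit in both statuses. An even split is the best case. Otherwise one status may be narrower, but the other is wider.

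**4. How far off are the inputs allowed to be?** At 5 vs 5 the gap closes only if the SD is at most 22.7/(1.687 × √0.4) = 21.3 g, or the CV at most 19.6%. At 4 vs 4 the values are 18.8 g and 17.4%.

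**5. What size would meet the limits in both statuses?** For UGE24, about 7 completers per cell (±21.4 g; 6 per cell gives ±23.3 g). For Cmax, about 6 per cell, which gives 0.810–1.234 and so matches 11.7 after rounding.

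**6. The overall model.** With five groups, diabetic status and covariates at 8 vs 8, the results are ±20.3 g (df 31) and 0.83–1.20 (df 33). If all 8 normal subjects are non-diabetic and the other groups split 4:4, they are ±21.6 g and 0.82–1.22. These figures assume that age, weight and fasting glucose are roughly balanced across groups. Variance inflation above (22.7/20.35)² = 1.24, or (22.7/21.58)² = 1.11 in the second case, would pass 22.7 g unless the covariates also reduce the residual SD.

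**7. The severe group.** In the overall model with 8 completers in every other group, severe vs normal for UGE24 is ±22.0 g with 6 severe completers, ±23.3 g with 5, ±25.0 g with 4 and ±27.7 g with 3.

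**The case against.** Much of the case on the other side stands.

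- **11.7 contains no error.** It names its comparison and is right for it. A reader might infer a miscalculation, but step 1 shows that there is none.
- **UGE24 is largely covered.** The overall model in SAP 6.1.3 has renal group as a factor, and its evident purpose is a comparison with normal. SAP section 2 also lists "Model estimated renal function comparison in UGE24, change from baseline and % change from baseline in UGE24" among the first results. What remains is a missing line of output specification, so it would be wrong to say that the UGE24 endpoint has the same gap as PK.
- **The PK gap can only be called not visible.** SAP 5.3 ends in a redaction, so the documents do not support saying that the plan has no pooled PK ratio. Nor does SAP section 2 settle it. For PK it lists "Summary statistics for PK parameters", but it also leaves out the by-status ratios that SAP 5.3 does plan. The protocol's visible text does list by-status ratios only.
- **By-status estimation is a legitimate choice.** No visible decision rule depends on these widths. At 11.7's own example of 42 g, the interval still excludes zero: 13.1–70.9 g at 4 vs 4 and 16.4–67.6 g at 5 vs 5.

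None of this supplies a visible PK contrast to which 0.81–1.23 applies in both diabetic statuses.

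**Conclusion.** The mismatch holds, mainly for PK. For Cmax, 11.7 quotes 0.81–1.23, while the listed ratios can at best have 0.77–1.30 (4 vs 4) to 0.79–1.26 (5 vs 5) in both diabetic statuses. On the UGE24 scale, the by-status half-width of 25.6–28.9 g is 13–27% above 22.7 g (25.6/22.7 = 1.13; 28.9/22.7 = 1.27). These are even-split figures, and an uneven split is worse in the smaller stratum. They rest on SD 24 g and CV 22% holding in both statuses.

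For UGE24 the residue is minor, because a planned model can deliver about ±20 g if covariates are roughly balanced.

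Two stronger readings are not supported. One is that the trial is too small: it was never sized for within-status precision, and what counts as adequate precision is the sponsor's judgement. The other is that ±22.7 g covers every impaired group: 11.7 states it for mild and moderate against normal only.

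Severity: minor to moderate.

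**What to change.** 1. **SAP 5.3, unless the redacted text already does so:** add an overall model for log Cmax and each AUC without the renal function by diabetic status interaction. Report the geometric mean ratio of each impaired group to normal with a 90% CI on Day 1 and Day 7. Keep the by-status ratios.
2. **SAP 6.1.3:** list the Day 7 difference of each impaired group from normal, with 90% CI, from the overall model already planned.
3. **Protocol 11.7:** state that its limits refer to the overall contrasts with at least 8 completers in both groups and, for UGE24, to mild and moderate against normal only. Add that severe against normal will exceed ±22.7 g if fewer than about 6 severe patients complete. Add that within one diabetic status the expected precision at an even split is about ±26–29 g and 0.79–1.26 to 0.77–1.30.

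**Cost:** one extra model per PK parameter and a few sentences. More enrolment is not proposed.

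**Downside:** the pooled contrast assumes a similar renal effect in both diabetic statuses. Protocol 3.2 expects diabetic status to have little impact on UGE24 but says nothing comparable for PK. The retained by-status contrasts let readers check the assumption.
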